Vital signs		X	X	X (Days 2, 4, and 6)	X	X (Days 10, 12 and 14)	X	X		X		X		Vital signs to be performed pre-dose. Temperature will be monitored every day during study participation. For further detail, see Section 8.1.2
12-lead safety ECGs		X	X	X	X	X	X	X	X	X	X	X		ECG should be performed pre-dose on dosing days. ECG timepoints may be reduced in subsequent dosing groups. For further detail, see Section 8.1.4
Testing for SARS CoV-2	X			X (Day 7)		X (Day 14)						X		An additional SARS-CoV-2 test will be performed approximately one week prior to admission to the unit. Weekly SARS-CoV-2 testing is required while in the unit (Days 7, 14) and on discharge (Day 20). An approved molecular

Procedure	Pre-Treatment Days		Week 1		Week 2		Week 3		In House Post Treatment Days					Notes
	Treatment Days		Treatment Days		Treatment Days									
	-2	-1	1	2, 3, 4, 5, 6, 7	8	9, 10, 11, 12, 13, 14	15	16 24h	17 48h	18 72h	19 96h	20 120h		
														Hours (h) relate to PK sampling post last dose
Drug/alcohol/nicotine screen	X													test (PCR) will be used. For further detail see Appendix 7 and Section 8.1.3
Haematology/Chemistry/Urine tests		X	X	X (Days 2, 4 and 6)	X	X (Days 9, 11 and 13)	X		X		X	X		For further detail, see Appendix 2
Pregnancy Test	X													Female participants only. For further detail see Appendix 2
VH3739937 Dose Administration			X		X		X							Weekly oral dose on Days 1, 8 and 15. Randomization to occur on Day 1 prior to dosing. For meal instructions prior to dose, see Section 5.3.1
Meals	Per site usual practice													
Plasma PK Sampling			X	X	X	X	X	X	X	X	X	X		2mL of blood will be collected at pre-dose (within 15 mins prior to dosing) and 1, 2, 3, 4, 5, 6, 7, 8, 9, 10, 12, and 16 h on Days 1, 8 and Day 15. The 24 h post day 1 dose collection on Days 2, 9 and 15 will be taken at post-dose collection timepoint. At all other timepoints on non-dosing days (Days 3, 4, 5, 6, 7, 10, 11, 12, 13, 14, 16, 17, 18, 19, 20), samples will be drawn at the post-dose

Procedure	Pre-Treatment Days		Week 1		Week 2		Week 3		In House Post Treatment Days					Notes		
	Treatment Days		Treatment Days		Treatment Days											
	-2	-1	1	2, 3, 4, 5, 6, 7	8	9, 10, 11, 12, 13, 14	15	16 24h	17 48h	18 72h	19 96h	20 120h				
Urine PK			X	X (Day 2, end of 24hr collection from Day 1)	X	X (Day 9, end of 24hr collection from Day 8)	X	X (Day 16, end of 24hr collection from Day 15)						Hours (h) relate to PK sampling post last dose		

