To characterize the population pharmacokinetics of VH3739937 and identify important determinants of variability, a population model was conducted as an alternate analysis approach to characterize the pharmacokinetics and the simulation was implemented to predicted the higher single dose and multiple dose cohort PK profile based on the model. The PK of VH3739937 following oral administration was adequately characterized by a linear one-compartment model with first-order absorption and first-order elimination, and with a dose factor and inter-individual variability on CL/F and on the magnitude of proportional residual error. The simulations for higher single dose 640 and 800 mg, multiple daily dose 50 and 100 mg and the multiple weekly dose 500 mg were conducted to predict the PK profile to obtain the Cmax and AUC for safety cover. More detailed information can be found in the Investigator's Brochure Supplement [GlaxoSmithKline Document Number [2021 RPS_CLIN_004025](#)].

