All participants will have a screening visit within 28 days prior to first dose and a follow-up visit approximately 28 days after the last dose. All dosing will be conducted in a hospital based inpatient clinical trial unit. Study participants will be confined to the clinic from Day -2 until discharge. Additional outpatient visits will be required for all study parts. Flexibility of visit scheduling may be required if a pandemic situation applies (see Appendix 7). Otherwise, study assessments will be performed as indicated in the SoA presented in this protocol.

A summary of the overall study design, including proposed doses, sample size, and order, is presented in Figure 3 and Figure 4 below.

Figure 3 Phase 1 Study in Healthy Participants using planned doses of VH3739937 Part 1 and Part 2

A=Active; P=Placebo

QD = once daily; QW = once weekly

*= Period 4 may include participants from both Cohorts 1 and 2

Highlighted cohorts and treatment periods denotes completed

The doses shown in [Figure 3](#) above are intended to demonstrate general concepts relating to factors of escalation. The modelling and simulation implemented using the data currently available following oral administration of a suspension formulation in the fed state indicated the predicted efficacious dose for the daily dose is 25 mg and the weekly dose is 500 mg. Due to the observed half-life of ~90 h, the anticipated accumulation ratio following repeated daily and weekly doses is ~6-fold and 1.3-fold, respectively. Dosing will be conducted in accordance with safety and PK stopping criteria (Section [7.1.4](#)).

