assessments will be performed as indicated in [SoA](#). Study participants will be confined to the clinic from Day -2 until discharge with requirement to complete all scheduled outpatient visits. Maximum duration of study participation from admission into the unit until completion of follow visit will be approximately 5 weeks.

Part 2 MAD: Dose Escalation

Dose escalation in Part 2 will be determined by the VH/GSK study team and the PI based on the double-blind (sponsor-unblinded) safety and PK data (minimally up to 15 days following the last dose) from the previous dosing Cohort (s). Specifically, safety and PK data through Day 29 in Cohorts 3 and 4 and through Day 33 in Cohort 5 from a minimum of five participants receiving active drug will be required for dose escalation.

Part 3 (RBA FE)

Part 3 will involve a randomized, open-label, single-dose, 3-period crossover optional Cohort 7 to compare the RBA of the GSK3739937 PiB with GSK3739937 Tablet and to assess the effect of food on the safety, tolerability and PK of GSK3739937 Tablet in healthy participants. In Part 3, approximately 18 participants will be treated to ensure that approximately 12 evaluable participants complete Cohort 7. If participants prematurely discontinue Part 3, additional participants may be randomized after consultation with the sponsor to ensure that approximately 12 evaluable participants complete the study.

[figure not shown]
Part 3 will consist of a screening period and 3 sequential treatment periods with a single dose of study intervention per treatment period.

Prior to dosing on Day 1 of Period 1, participants will be randomly assigned to 1 of 3 treatment sequences (ABC, BAC, or CAB). Participants will receive each of the following treatments administered as 1 treatment per period:

- Treatment A: GSK3739937 PiB, 100 mg (administered as oral suspension) administered under moderate fat conditions (reference)
- Treatment B: GSK3739937 Tablet, 100 mg (single dose given as 100 mg tablet(s)) administered under moderate fat conditions (test)
- Treatment C: GSK3739937 Tablet, 100 mg (single dose given as 100 mg tablet(s)) administered under fasted conditions (reference).

To ensure adequate washout, there will be at least 24 days between each dose of study intervention, with an allowance window of 4 hours (i.e., 24 days minus 4 hours) to allow flexibility in scheduling participants for dosing at the clinic.

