4.3.3. Part 1 (SAD) Starting Dose and Dose Escalation

The starting oral dose of VH3739937 in the SAD will be 10 mg. Assuming a 10-fold safety factor and a body weight of 70 kg, this starting dose is lower than that calculated based on the NOAEL in rat of 10 mg/kg/day (maximum recommended starting dose [MRS_D] = 11.3 mg) and the LOAEL in dog of 3 mg/kg (MRS_D = 11.7 mg), in the absence of a NOAEL in dog [[FDA/CDER](#), 2005]. Although a NOAEL was not established in the 4-week dog study due to the presence of gastric toxicity at all doses, the gastric findings at 3 mg/kg/day (LOAEL) were minimal in severity and reversible.

Based on the predicted human PK, a 10 mg dose would provide a mean AUC(0-inf) of 2.58 $\mu\text{g}^*\text{h}/\text{mL}$ and a mean Cmax of 0.0454 $\mu\text{g}/\text{mL}$. This predicted AUC(0-inf) is ~10-fold lower than that observed in the rat at the NOAEL (25.5 $\mu\text{g}^*\text{h}/\text{mL}$), 20.1-fold lower than that observed in the dog at the LOAEL (51.9 $\mu\text{g}^*\text{h}/\text{mL}$), and 37.3-fold lower than that observed in the rat LOAEL (96.2 $\mu\text{g}^*\text{h}/\text{mL}$).

Dose escalations in Part 1 (SAD) will be governed in real-time by safety and PK stopping criteria (see Section 7.1.4. and Section 7.1.5). Based on the assumptions described above, the top dose anticipated in Part 1 was a single dose of 640 mg. However, following review and evaluation of emerging available PK and safety data, a higher SAD dose of 800 mg was selected for evaluation in Cohort 1, Period 4. Observed exposures were lower than that projected and review of preliminary safety data from the SAD 10mg through to 640mg dose and the MAD 25mg dose, supported escalation to the 800mg dose. These preliminary PK and safety data are summarised in the IB Supplement [GlaxoSmithKline Document Number 2021 [RPS_CLIN_004025](#)]. The predicted median Cmax for 800 mg dose was 1.60 $\mu\text{g}/\text{mL}$. This higher 800mg dose will be in accordance with SAD PK stopping criteria. Based on the data collected from the observed doses so far in the study, the probability of any SAD participant having a Cmax $> 21 \mu\text{g}/\text{mL}$ is extremely low.

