- d. Equivalent to 21.0 µg/mL in human (based on 85% and 93% protein binding in dog and human, respectively).

Table 11 Projected steady-state PK for a range of potential QD (50-100 mg) or QW 500 mg doses following fed administration and comparison to efficacy target and preclinical exposure

Parameter	50 mg	100 mg	500 ^e mg
C_τ, µg/mL			
Median	0.905	1.57	0.429
Lower bound of 90% CI	0.557	1.01	0.253
C_τ/Ctarget (0.258 µg/mL)			
Lower bound of 90% CI	2.16	3.91	0.981
Cmax after last dose, µg/mL			
Median	0.968	1.72	1.5
Upper bound of 90% CI ^a	1.53	2.65	2.07
Cmax Cover with^b			
Dog 1-month GLP study (39.8 µg/mL) ^c	88.1	49.6	58.8
Dog CV study (9.82 µg/mL) ^d	21.7	12.2	14.5
Mean AUC, µg*h/mL			
Median	22.7	39.8	31.3
Upper bound of 90% CI ^a	36.1	62.0	45.5
AUC Cover with^b			
Rat NOAEL (25.5 µg*h/mL)	1.12	0.641	0.815
Rat LOAEL (96.2 µg/mL)	4.24	2.42	3.07
Dog LOAEL (51.9 µg/mL)	2.29	1.30	1.66

- a. The upper bound of the 95% PI is presented to capture the likely highest PK values.
- b. The Cmax and AUC cover were computed as the ratio of Cmax or AUC in animal divided by the median Cmax or AUC predicted in human.
- c. Equivalent to 85.3 µg/mL in human (based on 85% and 93% protein binding in dog and human, respectively).
- d. Equivalent to 21.0 µg/mL in human (based on 85% and 93% protein binding in dog and human, respectively).
- e. The weekly dose 500 mg
- f. the maximum 24 hour AUC were calculated from 0-24h after the last dose to match the daily safety limit 96.2 ug*h/mL

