8.3. Treatment of Overdose

For this study, any dose of VH3739937 greater than a planned dose level within a 20-hour time period will be considered an overdose.

Sponsor does not recommend specific treatment for an overdose. The investigator will use clinical judgment to treat any overdose.

In the event of an overdose, the Investigator should:

1. Contact the Medical Monitor immediately.
2. Closely monitor the participant for AE/SAE and laboratory abnormalities until study intervention can no longer be detected systemically (at least 5 days).

3. Obtain a plasma sample for PK analysis within 24 hours from the date of the last dose of study intervention if requested by the Medical Monitor (determined on a case-by-case basis).
4. Document the quantity of the excess dose as well as the duration of the overdosing in the CRF.

Decisions regarding dose interruptions will be made by the investigator in consultation with the Medical Monitor based on the clinical evaluation of the participant. No dose modifications are permitted without prior discussion and consent from the DEC.

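### Overdose definition (8.3): the single 20-hour window misses a full-size unscheduled dose given 20 h or more from any scheduled dose, chiefly in weekly Cohort 6 (minor)

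*Protocol*

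**What the plan says.** Protocol 8.3 opens by applying itself to the study as a whole and gives one definition: "any dose of VH3739937 greater than a planned dose level within a 20-hour time period will be considered an overdose". There is no variant by part or cohort. Four actions follow from an overdose: immediate contact with the Medical Monitor, close AE and laboratory monitoring, a PK sample if the Medical Monitor asks for one, and a CRF entry ("Document the quantity of the excess dose as well as the duration of the overdosing in the CRF").

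The same protocol contains three dosing patterns:
- Cohorts 3 to 5 are dosed every 24 h.
- Cohort 6 receives 500 mg every 168 h; SoA Table 5 specifies "Weekly oral dose on Days 1, 8 and 15".
- Parts 1 and 3 give one dose per treatment period. Successive doses are about 3 or 4 weeks apart in Part 1 and at least 24 days apart, less a 4-hour scheduling allowance, in Part 3.

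Protocol 10.3.1 uses the word overdose for AE reporting but does not define it. The SAP does not define it either.

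**The concern.** A 20-hour window is a natural choice for once-daily dosing, where it leaves 24 − 20 = 4 h of timing slack. It was not adapted when the protocol came to include a weekly cohort and single-dose periods. In those settings a second full dose on a non-dosing day puts no more than one planned dose level into any 20-hour window, so it passes the test. An oversized single dose is still caught everywhere; the gap concerns extra doses of ordinary size.

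What is at stake is a safety trigger. An administration error that 8.3 would be expected to cover would not formally set off the 8.3 actions, although most of the earlier dose would still be in the body given the long half-life.

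**Working it through.** **1. The plan's own figure.** The half-life comes from Protocol 4.1: "Due to the observed half-life of ~90 h". The accumulation ratio is 1/(1 − 2^(−τ/90)). For τ = 24 h, 2^(−24/90) = 0.831, giving 5.93 (protocol: about 6). For τ = 168 h, 2^(−168/90) = 0.274, giving 1.38 (protocol: 1.3). The half-life is therefore used here as the protocol uses it.

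**2. Coverage of the rule.** Take the planned dose level as the assigned dose. An extra full dose is flagged only if it falls less than 20 h from a scheduled dose. The uncovered time between two scheduled doses is max(0, τ − 2 × 20).
- Once daily: max(0, 24 − 40) = 0 h. An extra dose is never more than 12 h from a scheduled one.
- Cohort 6: 168 − 40 = 128 h, or 76% of the interval. Participants stay in the unit through Day 20, so both intervals count in full.
- After a final or only dose: SoA Tables 2 to 5 label the discharge day as 120 h after dosing, and Part 3 discharge is also on Day 6. Uncovered in-unit time is about 120 − 20 = 100 h. This applies after each single dose in Parts 1 and 3, after the last dose in Cohorts 3 to 5, and after the third weekly dose in Cohort 6.

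**3. Exposure after an unflagged repeat.** Protocol 2.2.1 describes the PK as "adequately characterized by a linear one-compartment model with first-order absorption and first-order elimination", so doses were superposed under C(t) = s·ka/(ka − k)·(e^(−kt) − e^(−ka·t)), with k = ln 2/half-life. The absorption rate is not in the documents. It is assumed to be 0.2 to 1.5 per h, with half-life varied over 75 to 105 h.

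*Cohort 6.* Doses fall at 0, 168 and 336 h. The scale s makes AUC(336–360 h) equal the Table 11 median of 31.3 µg*h/mL; footnote f there states that "the maximum 24 hour AUC were calculated from 0-24h after the last dose to match the daily safety limit". An extra 500 mg dose is added x hours after the third dose, and AUC is taken over the 24 h after it:
- x = 20 h: 49.6–55.2.
- x = 24 h: 48.8–54.1, or 1.56 to 1.73 times 31.3. At a half-life of 90 h: 49.6–52.8.
- x = 48 h: 44.8–48.1.
- x = 24 h, scaled to the Table 11 upper bound of 45.5 instead: 71.0–78.7.
- Cmax for x = 24 h: 2.18–2.42 µg/mL.

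One line of the grid: with half-life 90 h and ka 0.5 per h, the scheduled doses contribute 27.9 to that AUC and the extra dose 22.6, total 50.5.

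*Part 1, 800 mg.* Section 4.3.3 states: "The predicted median Cmax for 800 mg dose was 1.60" µg/mL. With the single-dose curve scaled to that Cmax, a repeat at 24 h gives 2.89–3.03 µg/mL, and a repeat at 20 h gives 2.94–3.07.

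The limits in Protocol 7.1.4 are AUC 96.2 µg*h/mL (MAD) and Cmax 21 µg/mL (SAD). Every value above is below its limit. The Cohort 6 medians at 20 to 24 h lie around the dog LOAEL of 51.9, which is not a stopping limit.

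**4. Model check.** At a half-life of 90 h the model gives a Cohort 6 trough of 0.40–0.47 µg/mL, which brackets the Table 11 median of 0.429. Across the whole grid it is 0.32–0.55, so the outer half-lives fit Table 11 less well.

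**The case against.** **The reading is optional.** In a window with nothing scheduled, the planned dose could be taken as zero, so any dose would exceed it. That is possible but less natural. The rule refers to a dose level, which Protocol 6.7 and 9.5 use for the steps of the escalation. On the zero reading the 20-hour limit would also do almost no work. A safety trigger should not depend on which reading site staff choose.

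**The error is unlikely.** This stands. Protocol 4.1 places all dosing in the inpatient unit. Under 6.5, preparation from bulk supply is confirmed by a second person, dosing is supervised, and dose and identity are confirmed by someone other than the person giving the dose.

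**Most 8.3 actions happen anyway.** This largely stands. Cohort 6 has PK samples and ECGs every day through Day 20 and laboratory tests about every second day. Parts 1 and 3 have PK samples at 24, 48, 72, 96 and 120 h, and 8.4 allows up to 10 extra samples. Section 8 requires immediate safety concerns to go to the sponsor, though that leaves a judgement to be made. What is lost is mainly the automatic Medical Monitor call and the CRF overdose entry.

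**Stronger readings a reader might infer.**
- That nearly all of the 3-to-4-week or 24-day gaps in Parts 1 and 3 are exposed. They are not: participants leave the unit on Day 6 and receive no drug as outpatients.
- That a repeat dose would go unrecorded. It would still be a protocol deviation (SAP 4.1), should appear in SAP Listings 9 and 18, and its time would be in source documents.
- That a repeat would breach an exposure limit. The projections do not show this. Table 11 already accepts an upper-bound AUC of 62.0 for planned 100 mg once-daily dosing, above the dog LOAEL.

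**Conclusion.** The definition is wrong as written, and the point is minor. It rests on the ordinary meaning of a planned dose level as the assigned dose. The formal gap is 128 of 168 h per weekly interval in Cohort 6, and about 100 in-unit hours after a single or last dose elsewhere. The once-daily cohorts are therefore covered between doses but not after the last one.

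The exposure figures are indicative only. They assume linear superposition, although the population model also has a dose factor on CL/F, and an absorption rate the documents do not give. No endpoint, analysis or stopping rule uses the overdose definition, so the trial's results are unaffected.

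**What to change.** Replace the definition in 8.3 with one sentence: an overdose is any dose of VH3739937 above the participant's planned dose level, or any dose not scheduled for that participant (including a second dose within 20 h of a scheduled once-daily dose), in all cohorts and treatment periods.

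This closes the gap in Cohort 6, in Parts 1 and 3, and after the last once-daily dose. A separate weekly window, such as 168 − 4 = 164 h, is not needed once every unscheduled dose counts. A scheduled dose brought forward within the Part 3 allowance remains a scheduled dose.

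The cost is one sentence at the next amendment, with no added procedures, visits or participants.

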8.4. Pharmacokinetics

- Whole blood samples of approximately 2 mL will be collected for measurement of plasma concentrations of VH3739937 at timepoints specified in the [SoA](#). Details of blood collection and processing of PK samples are detailed in the SRM.
- Whole blood samples of additional approximately 2 mL will be collected in SAD cohort 1 only for acidification purpose. Concentrations from acidified samples will be compared to concentrations from non-acidified samples and will be reported as exploratory data.
- The number of PK sampling time points may be reduced in the initial MAD cohort as well as further in subsequent MAD dosing groups once human PK data are available in the SAD as well as in the initial MAD cohorts.
- An additional 2 mL of whole blood samples will be collected for metabolite profiling of VH3739937 at the same timepoints as the PK samples on Day 1, Day 2, Day 14, Day 15 in MAD cohorts 3, 4 and 5, and on Day 18, and Day 19 in the MAD cohort 5 only, as specified in the [SoA](#). The results will be reported under a separate protocol. Details of blood collection and processing are detailed in the SRM.
- A maximum of 10 samples may be collected at additional time points during the study if warranted and agreed upon between the investigator and the sponsor. Instructions for the collection, processing, handling and shipping procedures of biological samples will be provided in the SRM. The actual date and time (24-hour clock time) of each sample will be recorded.
- In Part 1, Cohort 2 Period 3 only, pre-dose urine can be collected up to 3.5 h pre-dose for analysis of VH3739937 renal excretion. Afterward urine will be collected for analysis of VH3739937 renal excretion over 24 h collection periods as follows: 0-24 h, 24-48 h, 48-72 h, 72-96 h. Fresh spot urine collection will be taken at each outpatient visit. For further detail, please see SRM.
- In Part 2, urine PK and metabolite samples for analysis of VH3739937 will be collected at pre-dose (20 mL) (within 1 h prior to dosing) and from time 0 up to 24 h post dosing on Day 1 and from time 0 to 24 h post dosing on Day 14 in MAD Cohorts 3 and 4. Spot urine sample collection on Day 16, 17 18, and 19 at post dose timepoint used on Day 1. Fresh spot urine collection will be taken at each outpatient visit for urine PK sampling for analysis of VH3739937.

- In Part 2, Cohort 5, urine PK and metabolite samples for analysis of VH3739937 will be collected at pre-dose (40 mL) (within 1 h prior to dosing) and from time 0 up to 24 h post dosing on Days 1, 14 and 18. Spot urine sample collection on Day 20, 21, 22, and 23 at the post dose timepoint on Day 1. Fresh spot urine collection will be taken at each outpatient visit for urine PK sampling for analysis of VH3739937.
- In Part 2, Cohort 6, urine PK samples for analysis of VH3739937 will be collected at pre-dose (20 mL) (within 1 h prior to dosing) and from time 0 up to 24 h post dosing on Days 1, 8 and 15. Fresh spot urine collection will be taken at each outpatient visit for urine PK sampling for analysis of VH3739937.
- After PK analysis, aliquots of 200 mL pooled urine samples (0-24 h) will be used for metabolite profiling. A maximum of 2 urine samples may be collected at additional time points during the study if warranted and agreed upon between the investigator and the sponsor. The actual start and stop date and time (24-h clock time) as well as collected volume over 24 h will be recorded for urine sample. Details of PK urine sample collection, processing and handling, storage procedures and shipping procedures are detailed in the SRM
- Duodenal bile samples will be collected on Day 18 only for the analysis of VH3739937 and its metabolites for participants in MAD Cohort 5 only.
- The EnteroTest or EnteroTracker will be swallowed 2 h post-dose. After approximately 6.5 h the bile string will be removed. Bile fluid is recovered on a highly absorbent nylon line which is contained within a weighted gelatin capsule. The 140 cm EnteroTest line or 90 cm EnteroTracker line unwinds after capsule swallowing as the capsule dissolves in the stomach and the line then passes into the duodenum. During withdrawal, the weighted section of the capsule separates from the line and passes in the stool. Additional details of the bile EnteroTest/EnteroTracker sample collection, processing, storage and shipping procedures are provided in the SRM.
- The metabolite profiling of the plasma, bile and urine samples will be conducted under separate protocols and the results are reported separately according to the protocols.
- Residual plasma and urine samples from all cohorts after PK bioanalysis may be used for metabolite identification and profiling purpose.
- Drug concentration information that may unblind the study will not be reported to investigative sites or blinded personnel until the study has been unblinded.
- For Part 3, samples collected for VH3739937 plasma concentration may also be used to evaluate safety aspects related to concerns arising during or after the study. Once the plasma has been analysed for VH3739937, any remaining plasma may be analysed for other compound-related metabolites and the results reported under a separate protocol.

